5.2 Statistical Considerations and Sample Size

The primary goal of the study is to evaluate the safety and efficacy of the ExAblate palliative treatment of painful bone metastases. This study will be conducted with both the 1.5T and 3T MR scanners. Seventy (70) patients will be enrolled and treated; enrollment will continue at from 7-10 research sites.

A sample size analysis was performed using the McNemar Test Power Analysis from the PASS² program using parameters from the pivotal PMA study (PMA # P110039). The response rate in the USA was 18/30 = 60%. The proportion of non-responders experiencing pain progression was 30%. Thus, the proportion discordant was 90%. Given $\alpha = 0.025$ for a one-sided hypothesis, $1 - \beta = 0.7$ requires a sample size of 65 subjects to detect an odds ratio of 2.0. The odds ratio is equivalent to a difference between two paired proportions of 0.30 which occurs when the difference in the proportion of responders (60%) is 30% greater than the proportion of subjects experiencing pain progression (30%). In order to account for potential dropouts 70 subjects will be initially enrolled in the study.

The hypothesis can be specified as follows:

$H_0: P10 = P01$. $H_1: P10 > P01$, where $P10$ is the proportion of subjects that respond (improve by 2 points without increasing medications) and $P01$ is the proportion of subjects that worsen.

Subject Confidentiality

Subject confidentiality will be maintained throughout this study, including all publications. Data collected and entered into the CRFs are the property of the study sponsor. Representatives from the study sponsor or authorized sponsor representatives, the Institutional Review Board (IRB), Ethics Committee or the FDA may receive copies of the study records and may review medical records related to the study.

5.3 Missing Data

Analyses will be performed on both observed and data with missing values imputed per the method of last observation carried forward (LOCF) where data for missing visits is assigned the value of the previous visit. Analyses will include the presentation of results calculated based on the intent-to-treat principle.

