2.4 Study End Points

Safety

A full safety profile will be developed for the ExAblate treatment of bone metastases. All adverse events will be captured and summarized as defined in **Section-6.2**. Adverse events (type, frequency, severity) are expected to be similar to those captured for the original PMA study (PMA # P110039).

For his study, the Safety comparison with the data of the Pivotal (IDE Study G070022) study will be descriptive with no statistical endpoints.

Efficacy

A full efficacy profile will be developed for the ExAblate treatment of bone metastases. For this study efficacy will be determined by comparing outcomes at the 3 month visit to baseline within subjects. Additionally the safety and efficacy of treatment Responders and Non-Responders will be tabulated, and compared with that of the original PMA (P110039).

The primary endpoint is the proportion of responders at the 3 month study visit.

Definition of terms:

- Patient Responders: these are all ExAblate treated patients who experience at least a 2 point improvement from baseline on NRS at the treated site without increase in medications
- Patient Non-Responders: these are all ExAblate treated patients who experience less than 2 points improvement from baseline to 3 months on the NRS at the treated site without increase of medication or increased medications.
- Patient Pain Progression: these are all ExAblate treated patients who either experience 2 points worsening from baseline to 3 months on the NRS at the treated site or who increase morphine equivalence 25% or more. Pain progression is a subset of non-responders.

Secondary Endpoints

This study has two secondary end points. The goal of these secondary end points is to assess the impact of the ExAblate treatment of painful bone Mets on the overall quality of life and clinical benefits to ExAblate MRgFUS treated patients:

Quality of life outcomes of all treated patients will be captured during the course of the study. A comparison between baseline and 3 months post-ExAblate treatment of the BPI-QoL will be performed.

Pain Medications of all patients will be captured and summarized. Changes in narcotic medications will be expressed in morphine equivalents.

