13. Patients will have from 1 to 5 painful lesions and only the most painful lesion will be treated.
14. Patients with persistent distinguishable pain associated with 1 site to be treated (if patient has pain from additional sites, the pain from the additional sites must be evaluated as being less intense by at least 2 points on the NRS compared to the site to be treated).

Exclusion Criteria

1. Patients who either
 - Need surgical stabilization of the affected bony structure (>7 fracture risk score, see Section 7.4)

OR

 - Targeted tumor is at an impending fracture site (>7 on fracture risk score, see Section 7.4).

OR

 - Patients with surgical stabilization of tumor site with metallic hardware
2. More than 5 painful lesions, or more than 1 requiring immediate localized treatment
3. Targeted (treated) tumor is in the skull
4. Patients on dialysis
5. Patients with life expectancy < 3-Months
6. Patients with an acute medical condition (e.g., pneumonia, sepsis) that is expected to hinder them from completing this study.
7. Patients with unstable cardiac status including:
 - Unstable angina pectoris on medication
 - Patients with documented myocardial infarction within six months of protocol entry
 - Congestive heart failure requiring medication (other than diuretic)
 - Patients on anti-arrhythmic drugs
8. Severe hypertension (diastolic BP > 100 on medication)
9. Patients with standard contraindications for MR imaging such as non-MRI compatible implanted metallic devices including cardiac pacemakers, size limitations, etc.

10. Patients with an active infection or severe hematological, neurological, or other uncontrolled disease.
11. Known intolerance or allergies to the MRI contrast agent (e.g. Gadolinium or Magnevist) including advanced kidney disease
12. KPS Score < 60 (See “Definitions” below)
13. Severe cerebrovascular disease (multiple CVA or CVA within 6 months)
14. Individuals who are not able or willing to tolerate the required prolonged stationary position during treatment (approximately 2 hrs.)
15. Target (treated) tumor is less than 1cm from nerve bundles, bowels or bladder.
16. Patients initiating a new chemotherapy regime for pain purposes only, or radiation (for the targeted most painful lesion) within the last 2 weeks

Note: Planned multiple courses of chemotherapy are not considered New Chemotherapy.

17. Patients unable to communicate with the investigator and staff.

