 - a) Prior to the delivery of any treatment sonications, all patients **MUST** be adequately sedated for the treatment. Failure to adequately manage the patient may lead to unnecessary intra-procedure sonication related pain events. For this study, **ALL** patients must receive adequate level of local medication, for example, intercostal nerve block; failure to manage patients may also lead to under treatment. Note: equivalent methods of patient management may also be performed per local site standards.
 - b) Monitoring of heart rate and pO₂ saturation will be maintained throughout the procedure
 - c) During treatment, the nominal setting of the average of energy density for all treatment is set for 9 J/mm² ; While the treating

physician still has the ability to tailor the energy during the treatment, it should be noted that 1) lower energy densities may lead to under-treatment, 2) high energy levels requires appropriate anesthesia regimen selection to ensure patient comfort.

15. Sonifications will continue until the prescribed targeted area has been treated. The goal is that the total time from 1st to last therapeutic sonication will be limited to 180-minutes, or to patient tolerance.
16. **If no more than 3 planned sonifications can be performed using therapeutic energies**, then these patients will be considered as screen failures, and will NOT be included in the intent-to-treat analysis. However, they will be added to the Safety analyses
17. Criteria to terminate treatment include patient intolerance to the treatment, targeting difficulties due to patient motion or a decision of the treating physician
18. Immediately post-treatment, a series of MR scans will be performed. The scanning will include T2 weighted sequences and T1 weighted contrast enhanced sequences to evaluate general anatomy and to assess treatment effect.
19. The patient will be taken off the therapeutic table and escorted to a recovery area for observation period pending release from hospital.
20. All imaging exams taken during the study will be archived for later analyses

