4.4 Follow-up

The follow-up visits of all patients will be completed at 1 week and 1, 2 and 3 months post-ExAblate treatment. Patients will be evaluated for general health, efficacy measurements as well as for device/procedure related AEs that may have occurred during the follow-up period. Additional data regarding dosage and frequency of analgesic intake for the management of the

metastatic bone tumor induced pain will also be collected. Following treatment the study staff will mark the treatment NRS form indicating the place where the treatment was performed. These marked questionnaires will be provided to the patient to complete by the study staff for each time point in the follow up. The patient will be instructed to indicate the change of pain at the place of treatment. Although the 1-Week, 1-Month, 2-Month and 3-Month visits are office visits, and in view of the patient population general health may change at any given time due to the underlying cancer disease, participating sites may use their discretion to make the visit(s) a phone visit to accommodate the patient best interest. However, all attempts should be made to ensure an office visit. The visits will be used to evaluate the patient's NRS, BPI-QoL, and KPS, pain medication intake, symptoms and their general health, including any safety related issues and any changes in symptoms following treatment. For phone visits, study personnel will contact the patient, inquire about AEs and question the patient according to the pain questionnaire, and pain medication intake, and fill it out in parallel. Because the KPS is a physician completed assessment it may not be required for visits completed by telephone. The study personnel will then sign and date the completed forms.

All pre-treatment and post treatment MR and CT images will be de-identified and archived, and then will be forwarded to the Sponsor

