Study Enrollment at 50% Complete — As it was communicated to the agency during the PMA process as well as during the actual IDE study, the enrollment rate in the pivotal IDE study at US sites was approximately 0.07 subjects per month per site. The rate of enrollment was very slow partly because of the terminally ill patient population and their limited life expectancy, and partly because this particular patient population is heavily managed by their oncologists who tend to rely on pain medications and existing familiar technologies. However, in the pivotal IDE study, patients had the opportunity to receive an experimental palliative treatment that was not otherwise available. Now, since the PMA has been approved, patients can elect the ExAblate treatment without participating in the PAS; there may be less of an incentive to participate in the PAS than in the IDE study. Regardless, InSightec will use its best efforts to maintain a similar rate of enrollment in the PAS study as in the IDE study. Based on the pivotal study enrollment rate of 0.07, 1 site enrolled by 2 months, and adding 2 sites each 4 months to a total site enrollment of 10 sites (7 sites by the 6th month and 10 by the 14th month), the 70th subject would be enrolled by the 105th month of the study.

InSightec will continuously consider the possibility of increasing the number of participating sites; however, because of the large capital equipment investment and long installation time, it is expected that the number of sites that could be added to the study each year will be very limited, and would not meaningfully contribute to the increased rate of enrollment. Nonetheless, all newly installed sites will be offered an opportunity to participate in the PAS in an effort to maximize enrollment.

Final Study Report—Study results will be reported within 6 months of completion. Based on the timeline above, this is expected to be approximately 8 years and 10 months after full approval of the study.

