6.4 Criteria for Removal from the Study

Subjects can be exited from the study at any time if in the opinion of the principal investigator it is not in the best interest of the patient to carry on as planned. In Addition, patient may also chose to exit the study to pursue other alternative treatment options.

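### Section 5.3 names no missing-data analysis as primary for the 3-month endpoint, and no rule classifies patients who die or exit for other treatment before 3 months

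*Combined protocol and SAP*

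**What the plan says.** The endpoint is fixed in section 2.4: "The primary endpoint is the proportion of responders at the 3 month study visit". Section 5.2 tests H0: P10 = P01 against P10 > P01 at one-sided 0.025, where P10 is the proportion responding and P01 the proportion worsening.

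Section 5.3 is the whole missing-data plan. Analyses are to be run on observed data and again with gaps "imputed per the method of last observation carried forward (LOCF) where data for missing visits is assigned the value of the previous visit". It then adds: "Analyses will include the presentation of results calculated based on the intent-to-treat principle". No version is called primary.

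The intent-to-treat set is described only by who is left out. Of patients who receive no more than three planned therapeutic sonications, section 4.3 step 16 says "these patients will be considered as screen failures, and will NOT be included in the intent-to-treat analysis".

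The document expects early departures. Section 6.4 says a "patient may also chose to exit the study to pursue other alternative treatment options", and section 5.4 explains slow recruitment partly "because of the terminally ill patient population and their limited life expectancy". Three provisions limit the loss of data:

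- Section 3.2 excludes "Patients with life expectancy < 3-Months".
- Section 4.4 says "participating sites may use their discretion to make the visit(s) a phone visit to accommodate the patient best interest".
- Section 7 requires three contact attempts and a certified letter before a patient is treated as lost.

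**The concern.** The responder, non-responder and progression definitions in 2.4 all need a 3-month status, and none says what status a patient has after death or exit. The two planned versions fill that gap differently. LOCF keeps a patient who responded at month 2 and then died or left as a 3-month responder. The observed analysis removes the patient from numerator and denominator. Neither treats the event as a failure, and the intent-to-treat sentence says whom to analyse, not what value to assign.

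Two things are at stake. The responder proportion can be too high under LOCF. The P10-versus-P01 test can also be affected: a progressor carried as a responder adds one to P10 and removes one from P01, a shift of two patients. With about 70% planned power, a few patients matter. And because this is an open-label single-arm study, leaving the deciding version unnamed allows it to be chosen after the data are seen.

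**Working it through.** **Inputs (section 5.2).** P10 = 0.60, P01 = 0.30, discordant proportion 0.90, one-sided alpha 0.025, power 0.70, 65 required, 70 enrolled. The 30% progression rate is read as a share of all subjects, as the 90% discordant figure requires. The document gives no death or exit rate, so the number of exits k is an assumption, shown for 1 to 5. Five is the whole dropout allowance (70 − 65), not an expected exit rate.

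**The plan's own figure.** With pd = 0.90 and d = 0.30, the McNemar normal approximation is n = (z_α√pd + z_β√(pd − d²))²/d² = (1.960 × 0.9487 + 0.5244 × 0.9)²/0.09 = 60.4, so 61. With a continuity correction it is 64 or 67, depending on the form. Exact power at n = 65 is 69.3%, and the smallest n with 70% exact power is 67. The stated 65 therefore reproduces to within two patients.

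**Effect on one result.** The planned rates at n = 70 give 42 responders and 21 progressors. Suppose k of the 42 were last recorded as responders, then exited, and had in truth progressed. The p-value is the exact one-sided sign test, P(X ≥ r) for X ~ Binomial(r + w, 0.5), with r responders and w progressors.

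| k | LOCF | Observed | True status |
|---|---|---|---|
| 1 | 42/70 = 60.0%; 42 v 21, p = 0.0056 | 41/69 = 59.4%; 41 v 21, p = 0.0076 | 41/70 = 58.6%; 41 v 22, p = 0.011 |
| 3 | 42/70 = 60.0%; 42 v 21, p = 0.0056 | 39/67 = 58.2%; 39 v 21, p = 0.014 | 39/70 = 55.7%; 39 v 24, p = 0.038 |
| 5 | 42/70 = 60.0%; 42 v 21, p = 0.0056 | 37/65 = 56.9%; 37 v 21, p = 0.024 | 37/70 = 52.9%; 37 v 26, p = 0.10 |

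At k = 3 and k = 5 both planned versions reject and the true counts do not.

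**Type I error.** Full enumeration at n = 70 with P10 = P01 = 0.45, then exactly k patients recoded:

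- Correct coding: 1.9%.
- 1, 2 or 3 progressors carried as responders: 3.4%, 5.8%, 9.4% (five: 20.9%).
- 1, 2 or 3 progressors dropped: 2.6%, 3.6%, 4.9% (five: 8.6%).
- Mixed errors among five exits: three favourable and two unfavourable, 3.4%; two and three, 1.0%; all five unfavourable, 0.04%.

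**How long a relapse can go unseen.** The 2- and 3-month visits each have a window of ± 2 weeks (Table 1, section 4.5). An early month-2 visit and a late month-3 visit are one month plus four weeks apart, so the gap can approach two months.

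**Power of the proposed coding.** At 60% v 30% and n = 70, exact power is 73.0%. If 1, 3 or 5 true responders exit and become non-responders it is 68.8%, 60.1% or 51.4%.

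**The case against.** Four arguments on the other side have weight.

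*The planned versions may not disagree.* A reader might infer that LOCF and observed-case would give opposite decisions. The calculations do not show that: both reject at every k from 1 to 5 in the illustration. With five exits spread in the planned proportions, both give 60.0% (39 v 20, p = 0.009 observed; 42 v 22, p = 0.008 LOCF). Disagreement is possible, not demonstrated.

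*LOCF need not favour the device.* A reader might infer systematic inflation, or take 20.9% as the expected error rate. That figure needs five exits, all last recorded as responders and all truly progressed, and nothing in the documents supports that. A worse score or higher dose recorded before exit is carried forward as failure. A treatment-area pain flare, which section 6.2 lists among effects that usually settle within two weeks, could be carried forward from the 1-week visit. The mixed cases show how quickly the error falls back.

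*Relapse is not necessarily unrecorded.* Section 6.5 keeps progression leading to alternative treatment out of adverse event reporting, but pain scores and analgesic use are collected as efficacy data at every visit. That section does not show that relapse is lost from the efficacy dataset.

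*Failure is a choice of estimand.* The endpoint is pain at the treated site, and death from cancer after a documented local response is not self-evidently failed palliation. That stands: non-responder coding is a defensible composite, not the only possible one. But the plan must state some rule, and it states none. Phone visits, contact attempts and the life-expectancy exclusion reduce missing data; they do not classify a death or an exit.

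**Conclusion.** The point holds and should be fixed. Without any assumption, section 5.3 leaves the deciding analysis unnamed and the outcome after death or exit undefined; followed literally, LOCF makes some of these patients 3-month responders and observed-case removes them. Each patient carried as a responder is worth 1.4 points of the responder proportion, measured against a rule that counts such patients as non-responders.

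The effect on the test is conditional. Its size and direction depend on the number of exits and their last recorded status, which the documents do not give. The Type I figures are illustrative worst cases under H0: P10 = P01 as written in 5.2. They do not address the Efficacy text of section 5, which words the hypothesis as a margin of 30% or an odds ratio of 2 or more. On that wording 39 v 21 falls short: 39/21 = 1.86 and (39 − 21)/70 = 25.7 points. The comparison with the pivotal study is descriptive, so the consequence there is limited.

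**What to change.** In section 5.3, name one primary analysis of all treated patients in the intent-to-treat set and state that it alone decides the hypothesis. In it:

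- Patients who die, exit for other treatment of the treated site, or have no 3-month assessment are non-responders.
- They count as pain progression if their last recorded data meet the 2.4 definition. Those whose only such record is the 1-week visit are listed separately.

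State the limit of this coding. For exits without recorded progression it corrects the responder proportion and removes LOCF's false responders, but it gives the P10-versus-P01 test the same counts as observed-case. The dropped-progressor error rates above therefore remain for that test.

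Report as sensitivity analyses, not co-deciding tests: exits for other treatment counted as progression, a tipping-point analysis, observed-case, and LOCF (kept for the descriptive comparison with the pivotal study, whose own rule the documents do not give). In the k = 3 example, if all three exits were for other treatment, the primary test would be 39 v 21 (p = 0.014) and the progression sensitivity 39 v 24 (p = 0.038), so the report would show that the result depends on the exits. If the case report forms, which are not in the text, do not already do so, record the reason and date of exit.

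The cost is SAP wording, possibly one data field, a less favourable responder rate and the power loss shown above. The rule is also asymmetric, because a last-recorded progression is kept and a last-recorded response is not, even for a patient who merely missed the final visit. A 1-week flare can still be coded as progression, hence the separate listing.

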5.4 Study Timeline

The US study sites that participated in the recently approved pivotal study will be offered this protocol. New sites can only be added if ExAblate bone systems are installed. Because this entails a detailed review and approval process, new purchases and installations typically take a minimum of 12-20 months to complete. Thus, the timing for completion outlined below is premised on the assumption that the sites participating in

² Hintze, J. (2011). PASS 11. NCSS, LLC. Kaysville, Utah, USA. www.ncss.com.

this post-approval study (PAS) will be started with those already participating in the IDE investigation; should these sites accept to take part in this study. New sites will be added as needed and in compliance with the total number of sites approved for this study.

The following projections are our best evidence based estimates. These estimates will be updated in the progress reports to the FDA.

Facility Recruitment Complete — All available U.S. sites in the IDE will be offered participation in the PAS. All sites that accept will be included. This process will be completed within 3-6 months following final approval of the study.

Physician Recruitment Complete — As InSightec adds sites (i.e. sells more systems), we will offer them participation in the PAS. We will update the FDA of this effort in our progress reports, or per the agency instructions.

IRB Process Complete — The IRB process will be initiated within approximately 3 months after site participation has been confirmed.

Study Enrollment at 50% Complete — As it was communicated to the agency during the PMA process as well as during the actual IDE study, the enrollment rate in the pivotal IDE study at US sites was approximately 0.07 subjects per month per site. The rate of enrollment was very slow partly because of the terminally ill patient population and their limited life expectancy, and partly because this particular patient population is heavily managed by their oncologists who tend to rely on pain medications and existing familiar technologies. However, in the pivotal IDE study, patients had the opportunity to receive an experimental palliative treatment that was not otherwise available. Now, since the PMA has been approved, patients can elect the ExAblate treatment without participating in the PAS; there may be less of an incentive to participate in the PAS than in the IDE study. Regardless, InSightec will use its best efforts to maintain a similar rate of enrollment in the PAS study as in the IDE study. Based on the pivotal study enrollment rate of 0.07, 1 site enrolled by 2 months, and adding 2 sites each 4 months to a total site enrollment of 10 sites (7 sites by the 6th month and 10 by the 14th month), the 70th subject would be enrolled by the 105th month of the study.

InSightec will continuously consider the possibility of increasing the number of participating sites; however, because of the large capital equipment investment and long installation time, it is expected that the number of sites that could be added to the study each year will be very limited, and would not meaningfully contribute to the increased rate of enrollment. Nonetheless, all newly installed sites will be offered an opportunity to participate in the PAS in an effort to maximize enrollment.

Final Study Report—Study results will be reported within 6 months of completion. Based on the timeline above, this is expected to be approximately 8 years and 10 months after full approval of the study.

